The VRWP group will have VR with an instruction to increase their number of steps daily to at least 3,000 steps using the pedometer (VR plus walking plus pedometer group). They will receive pedometers (Fitbit Zip), instructions on how to use the pedometer, step log forms, with home instruction handout to walk more at least more than ten minutes at a time. This group will be instructed to wear a pedometer on or below the waist such as belt, waistband, or in trousers' pocket, during waking hours, all day, except for bathing or swimming. A clip designed to keep the Fitbit Zip clipped to the clothing will be provided. There is no charging time. Fitbit Zip uses a replaceable watch battery that can last up to 6 months. The participants will record on their activity log the number of steps shown on the step display at the end of the day. The Fitbit Zip will be device inclusive. Subjects will not be given instruction to program their information or synchronize their Fitbit Zip with an application software on a smart phone, tablet, or any computer device. The daily step log form will be given to the research staff every visit for recording. The research staff will encourage their participants to increase their daily steps at least 10% until they achieve at least 3,000 steps daily. The older adults in the group will be trained on how to use the pedometers before they take them home, and will have the opportunity to review this instruction with the research staff on consecutive visits if needed. There may be cost associated with the study in case of lost or malfunction from using the pedometer due to the subject will be encouraged but not required to replace the pedometer. The subject will continue to be the VRWP group and this situation will be reported in the discussion of results.

The VRW group will receive VR and a time-based instruction to walk more daily at least 10 minutes at a time (VR plus walking no pedometer group). This group will be instructed on the benefits of walking (similar to the first group) but will not be given the pedometer. They will have home instruction handouts to walk more at least more than ten minutes at a time and a walking log sheet. The research staff will instruct their participants to increase their daily time at least 10% until they achieve at least 30 minutes of walking exercise daily. The walking log sheet form will be given to the research staff by the participant every visit for recording.

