The VR (control) group will follow the conventional VR physical therapy without the encouragement of walking and without specification of walking in the home exercise program.

The use of an assistive device can be recommended for any subject in any group by the research staff to maximize safety. The patient may need to purchase the assistive device.

Participants who do not belong to the intervention group with pedometer will receive a pedometer after they completed the study. They will receive instructions on how to use the pedometer prior or on the day of their last visit.

Study Visits

For the experimental design that will be conducted at Florida Hospital locations, the following data will be collected as standard of care by the physical therapist during initial evaluation, and if more time is needed, during the first follow-up physical therapy appointment: mCTSIB, TUG, DGI, DHI, age, gender, body mass index, home situation, Functional Comorbidity Index (FCI) total, ability to drive, medications and insurance type. After the subject signs the informed consent, the study coordinator will be notified by the research staff to conduct a retrospective chart review on the physical therapy initial evaluation and first follow-up visit, if applicable, of the subject. The study coordinator will extract the following baseline measurements from the subject's medical record: DGI, mCTSIB, DHI, TUG and socio-demographic data that include age, gender, body mass index, home situation (lives alone or with social support), Functional Comorbidity Index (FCI) total, ability to drive (able or unable), medications for vertigo and insurance type (Medicare/Non-medicare). Based on the retrospective chart review, the study coordinator will determine if the subject is eligible to participate in the study.

Visit 1: Once the study coordinator determined that the subject is eligible to participate in the study, the subject will be assigned a research number and will be randomized into one of the three intervention groups. The research staff can initiate or continue the VR program. For the test-retest reliability of the TUG test, there will be one practice trial followed by two final performances that will be included in the data analysis. The subject will also be asked to complete the IPAQ-short form questionnaire. The test-retest reliability of TUG and the IPAQ-short form questionnaire are for research purposes only.

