Visit 2: The research staff can initiate the research intervention according to the intervention group.

Visit 3 to visit prior to discharge: The research staff can continue the VR and intervention according to the intervention group.

Discharge or last visit: All outcome measures (DGI, TUG, mCTSIB, DHI and IPAQ) will be reassessed. Discharge scores for DGI, TUG, mCTSIB and DHI are standard of care, while IPAQ is for research purposes only. The total number of visits and length of

interventions (in weeks) for every participant will be recorded as secondary outcome measures. These research data will be forwarded to the study coordinator, and will be stored in a locked cabinet and password protected Florida Hospital computer.

Four-weeks after discharge: The study coordinator will conduct a follow up phone call to all subjects four weeks after discharge summary is completed to obtain the level of physical activity using the IPAQ short form questionnaire. This is for research purposes only. A follow-up on a subject will be discontinued if a subject is not reached after three attempts of follow-up phone call made on three different days between 30 and 45 days. Data analysis will commence once all the data from 54 subjects are collected.

Table 1. Summary of Interventions for VRWP, VRW and VR Groups.

VRWP (n=18)	VRW (n=18)	VR (n=18)

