Analyses will employ five repeated measures Analysis of Covariance (ANCOVA), adjusting for age, with two independent variables (group and time) and five outcome measures (TUG, DGI, DHI, mCTSIB and IPAQ short form). The adjustment of age is based on age-related decline. Intraclass Correlation Coefficient will be calculated to establish the test-retest reliability of the TUG and a stepwise linear regression with age as covariate will be conducted for all 54 subjects at baseline to determine if TUG, mCTSIB and DGI are predictors of DHI. Two-tailed test will be utilized to compare the compliance with step log recording and meeting step goals between the two walking groups (VRWP and VRW), and ANOVA to compare of total number of visits and total length of intervention in weeks between the three groups. Alpha for all analyses will be set at 0.05 to test for significant difference.

Potential Risks and Benefits

Potential Benefits

Possible benefits include improved physical function.

Potential Risks

The addition of a prescribed walking program in the treatment of dizziness will challenge the subject's balance, and in rare cases may result in falls or more dizziness.

Performance-based outcomes such as mCTSIB, DGI, and TUG check for the subject's reaction whenever in a condition of unsteadiness. The risks associated with these tests are the potential for falls and for dizziness. Self-report questionnaires such as the DHI and IPAQ will need the subject to read the questions and recall past experiences. Looking down and reading the questions may provoke dizziness and eye strain. Other possible risks for subjects are: 1) finding the questions to be sensitive 2) emotional discomfort (uncomfortable/embarrassed/sad/tired) and 3) distress as subject thinks of experiences.

Mitigation of Risks

The research staff (treating physical therapist) will supervise the treatment at all times to minimize any such risks.

Provisions to Protect the Privacy Interest of Subjects

Subjects will be assigned research numbers for study-related records and data sharing. The patient's confidentiality will be protected by observing the HIPAA policies and procedures.

Early Withdrawal of Subjects

Investigator Withdrawal of Subjects

The PI may terminate the participation of the subject in the study if the subject may be in any danger or no longer meets the inclusion criteria of the study.

Subject Request for Withdrawal from Study

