Subjects may withdraw or take away the permission to use and disclose their health information for any reasons at any time. This can be done by sending a written notice to the PI. Information that has already been gathered may still be used or given to others, however no new health information that might identify the subject will be gathered after the subject withdraw from the study.

Data Collection and Follow-up for Withdrawn Subjects

Patients who request withdrawal or who are withdrawn by the PI from the study will have their information that has already been gathered and shared in the research database. These data will be included in the data analysis. The percentage of patients withdrawing will be calculated.

Adverse Event Reporting

At each therapy visit of the subject, the research staff/treating therapist will seek information if there is any adverse event caused by taking part in the study. In the event of a research-related injury, the subject should report this in person or by phone to the research staff/treating therapist and PI. All adverse events will be reported to Florida Hospital's IRB and Nova Southeastern University's IRB following their respective policies for reporting adverse events.

Safety Monitoring Plan

Safety Monitoring
N/A

Data and Safety Monitoring Board (DSMB) or Equivalent
N/A

Ethical Considerations

Subjects in the VRW and VR group will receive a pedometer after they completed the study.

Sharing of Results with Subjects

Results of the study that are part of standard physical therapy will be shared with subjects and referring physicians. Letters will be sent to all participants that contain the results of the research once the research is completed.

Funding Source

Application for funding will be done through the Adventist University in January 2018. The principal investigator is currently requesting managers to allow the allocation of her Continuing Education budget for 2018 for this study.

Subject Stipends or Payments

The pedometer will be donated to the 54 participants, who met the inclusion and exclusion criteria and randomized into one of the three treatment groups, as a reward for participating in the research study and for them to perpetuate their physical activity.

Publication Plan

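### Adverse events are actively sought only at therapy visits and only if judged caused by the study, and no by-arm table is planned, so falls are probably under-recorded and not safely comparable between arms

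*Combined protocol and SAP*

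**What the plan says.** - **The risk.** Potential Risks states that the prescribed walking will challenge balance and "in rare cases may result in falls or more dizziness".
- **Active enquiry.** Under Adverse Event Reporting, the treating therapist at each therapy visit "will seek information if there is any adverse event caused by taking part in the study".
- **Spontaneous reports.** The same section adds that after a research-related injury "the subject should report this in person or by phone to the research staff/treating therapist and PI". This route is not tied to a visit, but it too is limited by cause.
- **After discharge.** Study Visits describes one telephone call to every subject at four weeks, made "to obtain the level of physical activity using the IPAQ short form questionnaire". Table 1 and the study coordinator's duties under Resources Available also list only the IPAQ.
- **The arms.** The Randomization section sets out home walking for both walking arms; of the VRW group it says "They will have home instruction handouts to walk more". The control arm has conventional vestibular rehabilitation "without the encouragement of walking and without specification of walking in the home exercise program".
- **Analysis.** The data templates listed under Data Confidentiality, Storage, and Retention include no adverse event or falls file. Neither the Statistical Analysis Plan nor the closing Data Analysis section has a safety table or comparison. Safety monitoring and the DSMB are marked as not applicable.
- **Mitigation.** Mitigation of Risks says that the research staff "will supervise the treatment at all times to minimize any such risks".

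**The concern.** Both reporting routes ask for a causal judgement before an event is recorded. The Background says that older adults with dizziness fall more than others, so some falls should be expected in every arm whatever the treatment. Whether such a fall enters the record depends on whether the subject or the unblinded therapist links it to the study. That link is easier to make for someone who has been told to walk more.

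The stake is safety information, not efficacy. Counts collected under this rule could reassure falsely, because unattributed and post-discharge falls are missed. They could also suggest an excess in the walking arms that comes from attribution alone. In either case the report could not fairly describe falls by arm, although falls are the harm that the protocol itself names.

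**Working it through.** The documents give no fall rate, adverse event rate or safety power, so there is no planned figure to reproduce. The check is of the text, followed by illustrations on stated assumptions.

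**1. What each contact can capture, as written**
- Therapy visit: asked in all arms, filtered by cause. The number of visits is not fixed and is itself an outcome compared between arms, so opportunities to be asked may differ by arm.
- Spontaneous report: possible at any time, filtered by cause.
- Four-week call: made to all arms, with no question on falls or adverse events listed.

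With 54 subjects and at least four weeks each, 54 × 4 = 216 subject-weeks after discharge have no active enquiry, before any withdrawals.

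**2. Effect of the cause filter on a comparison**

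Inputs: 36 walking subjects (18 + 18) and 18 controls, from the Randomization section. Assumed: true fall risk p, equal in all arms, and the fraction c of falls judged study-caused.

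Expected recorded fallers = n × p × c. With p equal, the apparent risk ratio is c(walking) / c(control) and does not depend on p.

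| Assumed c, walking / control | Recorded, walking (p = 20%) | Recorded, control (p = 20%) | Apparent ratio |
|---|---|---|---|
| 100% / 100% | 36 × 0.20 × 1.0 = 7.2 | 18 × 0.20 × 1.0 = 3.6 | 1.0 |
| 50% / 50% | 36 × 0.20 × 0.5 = 3.6 | 18 × 0.20 × 0.5 = 1.8 | 1.0 |
| 80% / 20% | 36 × 0.20 × 0.8 = 5.8 | 18 × 0.20 × 0.2 = 0.7 | 4.0 |
| 60% / 10% | 36 × 0.20 × 0.6 = 4.3 | 18 × 0.20 × 0.1 = 0.4 | 6.0 |

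At p = 10% the 80% / 20% row gives 2.9 and 0.4; at p = 30% it gives 8.6 and 1.1. The ratio is 4.0 each time. So the filter lowers counts whenever c is below 1, and it biases the comparison only when c differs by arm.

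**3. What complete recording could support**
- Zero falls observed in n subjects leaves a two-sided 95% upper limit of 1 − 0.025^(1/n): 18.5% for n = 18 and 9.7% for n = 36. The one-sided limits, 1 − 0.05^(1/n), are 15.3% and 8.0%.
- Exact power of Fisher's test (two-sided 0.05, assumed control and walking risks): 10% v 20%, 0.060 (18 v 18) or 0.094 (36 v 18); 10% v 30%, 0.205 or 0.323; 20% v 40%, 0.159 or 0.250. For 80% power about 199, 62 and 82 per arm would be needed.

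These figures describe the sample size, not the recording rule. They show that even complete data support description only.

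**The case against.** The case on the other side has real force.

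- **Visits are not the only route.** A reader might infer that nothing is heard between visits or after discharge. The in-person or phone route contradicts that. What stands is that this route is passive and confined to research-related injury.
- **Falls during home walking before discharge are not simply lost.** Staff ask at every visit and collect the step or walking log then, and such a fall is the event most readily called study-caused. The likelier gaps are falls not attributed to the study and falls after discharge.
- **Control events can be attributed to the study.** A reader might infer that they almost never would be, so that counts differ by construction. The documents give no attribution rates. Potential Risks says the balance and gait tests carry a risk of falls and dizziness, and every arm has the TUG retest, which is done only for research. Differential attribution is plausible, not established.
- **No planned analysis is biased.** Comparative safety is not one of the four study purposes and no safety test is planned. This is correct. The gap is that the named harm has no cause-neutral record and no table by arm.
- **Unseen material.** Reporting follows the policies of two IRBs, and the visit chart and data collection flowsheet are not shown. They might ask for more, so confidence about actual recording is limited. The rule as written is still filtered by cause.
- **Supervision.** The statement can be read as covering clinic sessions only. On that reading it does not cover the home walking listed among the risks just before it, so the wording needs attention on either reading.

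**Conclusion.** The point holds as a limit on how adverse events are recorded and reported. Active enquiry is confined to therapy visits and to events judged study-caused, the only other route has the same causal limit, the existing four-week call asks nothing about falls, and no table by arm is planned. Under-recording of unattributed and post-discharge falls is probable, but it is an inference, and the documents give nothing to size it. Bias between arms depends on attribution differing by arm; the ratios of 4.0 and 6.0 rest wholly on assumed fractions and only show how large the effect could be.

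A reader might also infer that better recording would let the trial settle whether prescribed walking raises falls. It would not, with 18 per arm. The planned efficacy analyses are unaffected. The change is worth making because it is cheap and concerns the harm the protocol itself names.

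**What to change.** 1. At each visit and on the existing four-week call, ask all three arms the same fixed question: any fall, injury or worsening dizziness since the last contact, whatever the cause.
2. Record judged relatedness as a separate item, after the event is logged.
3. Add an adverse event file to the data templates. Tabulate by arm the subjects with at least one fall (exact confidence intervals), the number of events and the observation time. Observation time is needed because visit number and treatment length vary and are themselves outcomes. Label the table descriptive, with no test.
4. The closing Data Analysis section is written in the past tense. If data collection has ended, state the ascertainment rule in the report and draw no between-arm safety conclusion.
5. Separately, reconcile the supervision statement under Mitigation of Risks with the home walking programme in the Randomization section and Table 1.

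The cost is a few minutes per contact, more events to log, and one extra file and table. No new contacts are needed.

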All statistical analyses were performed using SPSS version 26. Mean and standard deviation were used to describe interval and ratio data, and frequencies for nominal data. Statistical significance was set at alpha <0.05. Since the parameters of a normal distribution were not met, nonparametric statistical tests were chosen for statistical analysis.

Objective 1. To evaluate the impact of walking as an exercise component of VR on both primary and secondary vestibular-specific outcome measures.

Mean and standard deviations on the mean differences of pretest and posttest of TUG, DGI, DHI, and mCTSIB were calculated to compare walking (VRWP + VRW) and control groups (VR only). P-value was calculated using the Kruskal-Wallis test to check for between-group differences in the primary and secondary outcomes. For within-group differences, the Wilcoxon Signed Rank Test was used to examine significant differences between the pretest and posttest.

Objective 2. To evaluate whether pedometers increase the adherence of older adults with vestibular issues to a walking program.

To compare the VRWP, VRW and VR groups, IPAQ-Walk and IPAQ-Total scores were categorized as improve, same or decline in pretest and posttest, posttest and four-weeks follow-up, and pretest and four-weeks follow-up. P-value was calculated using the Kruskal-Wallis test to check for between-group differences of sociodemographic data, IPAQ-Walk, IPAQ-Total, compliance in meeting step goals and compliance in step log. Friedman's 2-way ANOVA by ranks test was used to examine significant differences within the group.

Objective 3. To establish test-retest reliability of the TUG test on older adults with dizziness.

Intraclass Correlation Coefficient (ICC) was calculated using the two-way mixed model, consistency type on a single measure model with a 95% CI for relative reliability. For absolute reliability, the Standard Error of Measurement (SEM), Minimal Detectable Change (MDC) 95% CI, and Bland-Altman 95% level of agreement were examined. The SEM provides the range of scores on retesting. A smaller value of SEM means the calculated score is close to the true score.⁴⁴ The MDC is used to reflect the true change in score that exceeded the errors of measurements. Both the SEM and MDC are the same units of the original measures, which allows easier interpretation of results when applied in the clinical practice.⁷⁴

The Bland-Altman plots show the distribution of the difference scores of two measurements around zero. The 95% level of agreement means that 95% of the difference scores fall within two standard deviations above or below the mean of the difference scores. Values closer to zero means greater reproducibility between two repeated measures.

Objective 4. To investigate if the TUG, DGI, and mCTSIB are significant and strong predictors of the DHI in older adults with dizziness.

The subjects were then grouped based on the DHI test results, using the categories suggested by Whitney et al: 0-30 for mild, 31-60 for moderate, and 61-100 for severe.¹⁰⁴ This analysis is similar to the work of Vereeck et al⁸⁴ to obtain a better picture between the dependent variable DHI and the independent variables: mCTSIB, TUG, and DGI. Kruskal-Wallis analysis was calculated to compare group means for age, mCTSIB, TUG, and DGI. The significance values were adjusted by the Bonferroni correction for multiple tests.

Before the multiple linear regression analysis, assumptions were tested to establish the nature of the data. The obtained Durbin-Watson statistic for the analysis of the independence of

observations is 2.639. The Durbin-Watson statistic can range from 0 to 4, with a value of approximately 2 to indicate that there is no correlation between residuals. The obtained value is close to 2, therefore it can be accepted that there is the independence of observations. The assumptions of homoscedasticity, normality, and multicollinearity are upheld. There is no presence of outliers in the data.

The Spearman Rho correlation coefficients were calculated to establish the relationships between the DHI and mCTSIB, TUG and DGI. As a general guideline, the value 0.00 to .25 indicates little to no relationship, 0.25 to 0.50 suggests fair relationship, 0.50 to 0.75 denotes moderate to good relationship and above .75 is considered good to excellent relationship.⁴⁴ Then, a multiple linear regression analysis was conducted for a continuous dependent variable and three independent variables to identify the predictors of DHI.

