Subject Enrollment			X	X	X	X	X	X
Data Collection			X	X	X	X	X	X
Data Analysis								
Interpretation								
Dissemination								

Month	Task	2018 July	Aug	Sept	Oct	Nov	Dec	2019 Jan
IRB								

Submission							
Protocol Set							
Completion of Training Requirements by Research Personnel							
Subject Enrollment	X	X					
Data Collection	X	X					
Data Analysis			X	X			
Interpretation			X	X			
Dissemination					X	X	X

Materials of Human Origin: Collection, Preparation, Handling and Shipping

N/A

Study Outcome Measures (Endpoints)

The DHI is a 25-item self-report questionnaire that quantifies the functional, emotional and physical impact of dizziness. Answers are graded 0 for no, 2 for sometimes and 4 for yes, with a maximum total score of 100. Interpretations are mild dizziness for scores between 0-30, moderate for 31-60 and severe for 61-100.³² DHI has been found to have excellent negative correlation ($r=-0.64$) with the Activity Specific Balance Confidence Scale (ABC) in the elderly.³⁹ For the population with vestibular dysfunction, it has excellent correlation with ABC ($r=-0.64$)³⁹ and SF-36 ($r=0.53-0.72$),⁴⁰ and moderate statistically significant negative correlation with Sensory Organization Test conditions 2 ($r=-0.39$), 4 ($r=-0.36$), 5 ($r=-0.42$) and 6 ($r=-0.35$).⁴¹ The Minimal Detectable Change (MDC) for peripheral and central vestibular pathology is 17.18 points and the Minimally Clinically Important Difference (MCID) for vestibular dysfunction is at least 18 points between the pretreatment and post-treatment scores.³² The MDC and MCID scores for older adults with dizziness are not established.

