The principal investigator may share the research data with accreditation organizations and regulatory agencies, dissertation committee, and publications, medical meetings, or scientific journals for the purposes of completing the research study, and analyzing and evaluating the results. Individual patients (subjects) will not be identified during data sharing, and a research number will be used instead during the data sharing process, unless necessary to carry out the research study or required by law.

Sample Size Determination

A priori power analysis predicting a large effect size ($F=.25$) determined that a total of 54 subjects (18 in each group), who met the inclusion and exclusion criteria will be needed, with alpha at the conventional value of .05 to achieve a .80 power, that includes an assumption of a dropout rate of 10% .

Statistical Analysis Plan

The results will be presented through the following tables with supporting explanations:

- Clinical and sociodemographic characteristics of participants by group at baseline.
- Comparisons of TUG, DGI, mCTSIB and DHI between the three intervention groups on admission and discharge.
- Comparisons of self-reported walking activity (walking MET-min/week) and total self-reported energy expenditure (total physical activity MET-min/week) as determined from the IPAQ short form on admission, discharge and four-week follow-up between the three intervention groups
- Comparisons of averages of compliance to step log recording and compliance rate for meeting step goal between the VRWP and VRW groups. Compliance is defined as low (<33%), moderate (33%-75%) and high (>75%) based on the step log or walking log. This grading of compliance was used by Hall and colleagues in their research on efficacy of gaze stability exercises in older adults with dizziness.⁵³
- Comparisons of total number of visits and length of interventions in weeks between the three intervention group.
- Intraclass Correlation Coefficients for the Timed Up and Go test-retest reliability
- Result of stepwise linear regression analysis for TUG, DGI, mCTSIB and DHI

All interval and ratio data will be tested for normality prior to undertaking the data analysis. Descriptive statistics will be used to describe the characteristics of the sample and compare the three groups at baseline. This will include Analysis of Variance (ANOVA) for parametric and Chi Square for nonparametric sociodemographic and clinical data.

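### No version of the Objective 1 analysis uses a primary outcome's admission score as a covariate, so the walking v VR comparison is valid but may be less precise than the data allow

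*Combined protocol and SAP*

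**What the plan says.** The documents hold two versions of the Objective 1 analysis.

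- **Protocol, Statistical Analysis Plan:** "Analyses will employ five repeated measures Analysis of Covariance (ANCOVA), adjusting for age, with two independent variables (group and time"). Age is the only covariate named. The admission score enters as one of the repeated measurements.
- **Data Analysis section:** the parametric plan is dropped: "Since the parameters of a normal distribution were not met, nonparametric statistical tests were chosen for statistical analysis". Under Objective 1, "Mean and standard deviations on the mean differences of pretest and posttest of TUG, DGI, DHI, and mCTSIB were calculated" to compare the pooled walking groups (VRWP + VRW) with VR. Then "P-value was calculated using the Kruskal-Wallis test to check for between-group differences in the primary and secondary outcomes". The section does not say whether the ranked values are the differences or the discharge scores.

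The admission scores are available. Study Visits has the study coordinator extract from the "medical record: DGI, mCTSIB, DHI, TUG and socio-demographic data that include age", and this happens before randomisation.

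**The concern.** When an outcome is measured before randomisation and again at the end, its own baseline is usually the strongest predictor of the final value. Using it as a covariate with an estimated coefficient removes noise that the groups share. The two versions here do something else. A change score, and equally a group-by-time test with two time points, subtracts the baseline with the coefficient fixed at 1. A test on discharge scores alone does not use it at all. Neither is efficient throughout: change is weak when rho is low or many patients sit near a scale limit, and discharge alone is weak when rho is high.

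The trial is small: 54 patients, about 48 after the assumed dropout, split 2:1 once the walking arms are pooled. A real walking effect could be missed more often than it need be, and a null result would then be harder to interpret. Non-normality does not force covariates out, because rank ANCOVA keeps them. The move to Kruskal-Wallis dropped even the planned age adjustment.

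**Working it through.** **Inputs from the documents.** Allocation 18:18:18, so 36 v 18 when pooled (Randomization). Sample Size Determination: "predicting a large effect size ($F=.25$) determined that a total of 54 subjects", alpha .05, power .80, "that includes an assumption of a dropout rate of 10" percent. Bounded scales (Study Outcome Measures): DHI "with a maximum total score of 100", DGI maximum 24, mCTSIB timed for 30 seconds.

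**Inputs assumed, because the documents do not give them.** Rho from .3 to .9; SDs, admission means and gains for the bounded scales.

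**The plan's own figure.** 54 cannot be confirmed from the stated inputs, because the number of time points and rho are missing. A group-by-time test at f = .25 needs 48 with two time points and rho .45 (or three and rho .3), and 48/0.9 = 53.3, which rounds up to 54. A one-way F at f = .25 needs 158 before dropout. The concern does not depend on this figure.

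**Step 1, variance.** In units of SD²(1/n1 + 1/n0), with equal SDs: discharge alone = 1; change = 2(1 − rho); ANCOVA = 1 − rho². ANCOVA relative to change is (1 − rho²)/(2(1 − rho)) = (1 + rho)/2, which is 0.65/0.75/0.85/0.90/0.95 at rho .3/.5/.7/.8/.9.

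**Step 2, effect and arms.** Read as a between-group effect at 2:1, f = .25 is d = .25/√((2/3)(1/3)) = 0.530 SD. 54 less 10% is 48.6, taken as 32 v 16, so √(1/32 + 1/16) = 0.306.

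**Step 3, the protocol model.** Noncentral t power for the two-group contrast, with ANCOVA on 44 df and its variance multiplied by 1 + 2/44 for chance imbalance on two covariates:

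| rho | .3 | .5 | .7 | .8 | .9 |
|---|---|---|---|---|---|
| group-by-time | 0.30 | 0.40 | 0.59 | 0.76 | 0.97 |
| ANCOVA | 0.41 | 0.48 | 0.64 | 0.79 | 0.97 |

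**Step 4, the rank tests.** Monte Carlo, 20,000 trials per cell, two-sided 0.05, tie-corrected Kruskal-Wallis (KW). Rank ANCOVA is Quade's method: a t test on the residuals of ranked discharge regressed on ranked admission and ranked age. Age is simulated as unrelated to outcome, so its cost is charged with no gain.

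| Scenario | Test | .3 | .5 | .7 | .8 | .9 |
|---|---|---|---|---|---|---|
| Normal, no limits | KW on change | 0.28 | 0.38 | 0.56 | 0.74 | 0.96 |
| | KW on discharge | 0.37–0.38 | 0.37–0.38 | 0.37–0.38 | 0.37–0.38 | 0.37–0.38 |
| | Rank ANCOVA | 0.40 | 0.45 | 0.58 | 0.72 | 0.92 |
| 0–24 scale, mean 18, SD 4, gain 2 | KW on change | 0.22 | 0.28 | 0.41 | 0.53 | 0.75 |
| | Rank ANCOVA | 0.38 | 0.43 | 0.56 | 0.68 | 0.88 |
| 0–24 scale, mean 12, SD 4, gain 2 | KW on change | 0.28 | 0.38 | 0.55 | 0.73 | 0.94 |
| | Rank ANCOVA | 0.39 | 0.45 | 0.59 | 0.72 | 0.92 |
| DHI, mean 30, SD 20, gain 18 | KW on change | 0.17 | 0.21 | 0.28 | 0.36 | 0.51 |
| | Rank ANCOVA | 0.36 | 0.41 | 0.52 | 0.63 | 0.81 |
| DHI, mean 60, SD 20, gain 18 | KW on change | 0.28 | 0.37 | 0.55 | 0.72 | 0.94 |
| | Rank ANCOVA | 0.39 | 0.45 | 0.59 | 0.72 | 0.93 |

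The DHI gain of 18 is the MCID in the protocol, and 30 and 60 are its category limits. At DGI-type mean 18, 8.5% are at the maximum on admission and 19% of VR at discharge. At DHI mean 30, 7% are at zero on admission and 29% of VR at discharge.

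Without limits, the gain over KW on change is about +11/+8/+3/−2/−3 points. The gain over KW on discharge is +2/+8/+21/+34/+54. In the two scenarios near a limit, the gain over change is 13 to 30 points and does not vanish at high rho.

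**Step 5, validity.** Type I error was 0.046 to 0.055 in every cell, so the existing tests are sound on this point.

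**The case against.** Five points deserve weight.

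1. **It is not an error.** The tests are unbiased and hold their level, and a post hoc addition cannot restore power to a test already reported. This stands, and it limits the claim to precision.
2. **The admission score is not ignored.** On the natural reading it is subtracted. This stands too: the accurate statement is that it is never a covariate with an estimated coefficient.
3. **The largest gains need the less likely reading.** The +21 to +54 points apply only if discharge scores were ranked. On change, without limits, the rank method gains 3 points at rho .7 and loses 2 to 3 at .8 and .9. This stands, and it is why the tested variable must be named.
4. **The effect may be larger.** The group-by-time reading of f, which can reach 54, implies .5/√(2/9) = 1.06 SD. Without limits, KW on change v rank ANCOVA is then 0.78 v 0.92 at rho .3, 0.91 v 0.96 at .5 and 0.99 v 0.99 at .7, so the gain is slight from rho .5 up. Near a limit it persists: 0.68 v 0.93 at rho .5 (0–24 scale, mean 18) and about 14 points at rho .7.
5. **The limit scenarios are assumed.** The documents give no admission means or SDs. mCTSIB and TUG skewness were not part of these scenarios. This stands, so no outcome can be ranked as the most affected.

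**Conclusion.** The concern holds as a point of efficiency. Neither the protocol model nor the Data Analysis section conditions TUG, DGI, DHI or mCTSIB on its admission score, and the score is to hand for all four.

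If change was tested and scores lie away from the scale limits, the cost is about 11 points of power at rho .3, 8 at rho .5, and nothing from about rho .8. If many patients sit near a limit, it is 13 to 30 points in the scenarios tried. If discharge scores were tested, it grows from 2 points at rho .3 to 54 at rho .9. All of this rests on an assumed rho, assumed score distributions, a 0.53 SD effect and 32 v 16 analysed. Validity is affirmed for this point only, not for other features of the analysis.

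**What to change.** - State which values the Objective 1 Kruskal-Wallis test ranked: differences or discharge scores.
- For each of the four primary outcomes, compare walking with VR on the discharge score by rank ANCOVA (Quade), with the admission score and age as covariates.
- Report beside it the ANCOVA-adjusted mean difference with a bootstrap 95% interval. The p-value comes from ranks and the interval from means, so say that the two can disagree.
- If the Data Analysis section describes completed work, as its past tense suggests, keep the reported test and label the addition a post hoc sensitivity analysis.
- Report by arm the share of patients at the DGI and mCTSIB maximum at admission. Adding the share at zero on the DHI, and the discharge figures, would show whether the limit scenarios apply.

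**Cost.** A re-run on data already extracted. The covariates use one or two degrees of freedom, about 2% to 5% of variance at N = 48 (1/45 to 2/44). If change was tested, rho is about .8 or more and scores are away from a limit, the rank method gains nothing or loses 2 to 3 points. The percentile bootstrap covered 92% to 94% at 32 v 16, so its interval is slightly narrow.
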